1.0 TRIAL OUTLINE

Study Title	Transcutaneous Electrical Spinal Stimulation (tSCS) for Improving Upper Limb Function in People with MS
Study Registration	TBD
Study Category	Interventional
Phase	Pilot study
Background & Rationale	The ability to efficiently use their hands is critical for maintaining activities of daily living (ADLs), a crucial unmet need for people with MS (PwMS). Recent clinical trials in patients with spinal cord injury have shown excellent safety and provided evidence of efficacy that tSCS associated with occupational therapy can improve the upper limb (UL) function and the ability to perform ADLs. Therefore, we propose to test the efficacy of tSCS in a pilot study in PwMS with moderate to severe UL disability.
Study Design	Double-blind, parallel, randomized, two arms, sham-controlled study in patients with MS and with significant disability of the upper limbs treated with tSCS and occupational therapy
Objective(s)	To assess the safety and efficacy of tSCS as add-on to standard rehabilitation in MS patients with moderate to severe UL disability
Outcome(s)	
 Primary endpoint: differences in the nine-hole peg test (9-HPT) affected hand in the tSCS treated vs. sham groups by the end of treatment (V3 vs V5) Secondary endpoints: 
 Percentage of responders: 20% difference on the 9HPTd (minimal clinically important difference (MCID)) from baseline to end of the study Change in the 9HPT dominant and non-dominant hand from baseline to end of the study Change in the Action Research Arm Test (ARAT) from baseline to end of the study Change in the modified Ashworth Scale (mAS) for spasticity assessment from baseline to end of the study Hand strength measured by Grip and Pinch force dynamometers from baseline to end of the study Change in the NeuroQOL Upper Extremity function from baseline to end of the study Change in the Modified Fatigue Impact Scale (MFIS) from baseline to end of the study

	
9. Change in Global Impression of change (GIC) from baseline to end of the study
 
Safety and Tolerability
 
 1. presence of serious adverse events 2. Retention rate 3. % sessions attended
Inclusion / Exclusion Criteria	
Inclusion: Patients with MS and moderate to severe UL disability defined as 9HPT affected hand ≥ 33.4 sec; 21 to 65 years old
 
Exclusion: patients with relevant comorbidities, pacemakers or metal implants

Measurements & Procedures	
 1. tSCS 2. Occupational Therapy 3. Clinical scales and PROs
Study Product / Intervention	tSCS is a non-invasive electric stimulation system that has shown good tolerability and signs of efficacy for improving UL disability
Controls	Sham (fictitious stimulation) will be used as control arm
Number of Participants & Rationale	
N=60 (30:30)
 
Rationale: accepting an alpha risk of 0.05 and a beta risk of 0.1 in a two-sided test, 10 subjects are necessary in each group to recognize as statistically significant a minimum difference of 10 units on the 9HPT scale between any pair of groups assuming that 2 groups exist. The common deviation is assumed to be 5.5. It has been anticipated a drop-out rate of 10%.

Study Duration:	
24 months
 
6 months recruitment, 9 months randomized phase, 6 months OLE, 3-month analysis and clinical scientific report

Timelines:	
 ● First Patient First Visit (FPFV): January 1st, 2025 ● Last Patient Last Visit (LPLV): December 30th 2026
Study Schedule:	
Patients in Spain are recruited from the three MS centers (Hospital del Mar, Hospital Clínic and Hospital Sant Pau) in Barcelona and treated in a single therapy center at Hospital del Mar located closely to all of them. Patients in the Netherlands are recruited at the Rijndam center, Erasmus Medical Center.
 
Run-in period (6 weeks with occupational therapy)
 
Double-Blinded period: 6 weeks for safety and efficacy assessments

	Open Label Extension (6 weeks) for safety and durability of efficacy
Study Center:	Hospital del Mar (HMar); Hospital Clinic of Barcelona (HCB); Hospital Sant Pau (HSP), all in Barcelona, Spain; Rijndam center, Erasmus Medical Center (EMC)
Statistical Analysis Plan	
The primary and secondary endpoints will be assessed using linear mixed-effects models (LME). These models will include the outcome measure as the dependent variable, and treatment group, time, and their interaction as independent variables, with random intercepts for participant and site to account for the longitudinal and clustered nature of the data.
 
Populations : 1) Intention to treat population; 2) Per protocol population: patients that completed 70% of the therapeutic sessions

A list of abbreviations used in this document can be found in Appendix 12.3.

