	
5. Hand strength measured by Grip and Pinch force dynamometers (Figure 10)
 
6. Change in the NeuroQOL Upper Extremity function from baseline to end of the study
 
7. Change in the Modified Fatigue Impact Scale (MFIS) from baseline to end of the study
 
8. Change in Global Impression of change (GIC) from baseline to end of the study

Exploratory endpoints	
Statistical Methods for Key Efficacy Analyses	Linear mixed-effects models will be used to test the association between treatment arm and all primary and secondary endpoints.
Statistical Methods for Key Safety Analyses	Descriptive statistics
Interim Analyses	No interim analysis for efficacy or safety is planned for this study.
Multiplicity	Not planned
Sample Size and Power	
Sample size: n=60
 
For a large, standardized effect size (Cohen's $d=0.8$), with a sample size of 52 (26 in each arm) we would have greater than 80% power to detect a significant difference in 9HPT between treatment arms using a two-sample t-test and a two-sided significance level of 0.05. Assuming a common standard deviation of 5.5, this corresponds to a difference of 4.4 units between treatment groups. Allowing for a conservative attrition rate of 15% (our previous trial in SCI with a similar design had 10% attrition⁴⁻⁶), we plan on enrolling 60 participants.
 
Furthermore, as our proposed analysis is a linear mixed-effects model, we anticipate greater efficiency resulting in a slightly higher power. Reimbursement of travel expenses will be used to promote retention.

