8.9 Sample Size and Power Calculations

Sample size

Sample size: n=60

Power for the primary hypothesis

For a large, standardized effect size (Cohen's $d=0.8$), with a sample size of 52 (26 in each arm) we would have greater than 80% power to detect a significant difference in 9HPT between treatment arms using a two-sample t-test and a two-sided significance level of 0.05. Assuming a common standard deviation of 5.5, this corresponds to a difference of 4.4 units between treatment groups. Allowing for a conservative attrition rate of 15% (our previous trial in SCI with a similar design had 10% attrition⁴⁻⁶), we plan on enrolling 60 participants. Furthermore, as our proposed analysis is a linear mixed-effects model, we anticipate greater efficiency resulting in a slightly higher power. Reimbursement of travel expenses will be used to promote retention.

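### The synopsis and Section 8.9 justify the same 60 patients with incompatible calculations; the synopsis inputs lead to about 18 to 24 patients

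*Protocol*

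**What the plan says.** The Trial Outline in Section 1.0, under the number of participants, gives 60 in a 30:30 split. Its rationale is that "10 subjects are necessary in each group to recognize as statistically significant a minimum difference of 10 units on the 9HPT scale". The error rates behind this are a two-sided alpha of 0.05 and a type II risk of 10%, that is 90% power. On the SD it says "The common deviation is assumed to be 5.5", and on losses "It has been anticipated a drop-out rate of 10" per cent.

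Section 8.9, repeated in Table 4 of Section 8.1, justifies the same 60 differently. It takes a standardized effect of 0.8 and states that "with a sample size of 52 (26 in each arm) we would have greater than 80% power" with a two-sample t-test at two-sided 0.05. It continues: "Assuming a common standard deviation of 5.5, this corresponds to a difference of 4.4 units between treatment groups". On losses it says "Allowing for a conservative attrition rate of 15" per cent, and notes for comparison that "our previous trial in SCI with a similar design had 10% attrition".

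The two places agree on the total, alpha, sidedness and SD. They disagree on the other four inputs:

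| Input | Section 1.0 | Section 8.9 and Table 4 |
|---|---|---|
| Target difference | 10 units | 4.4 units |
| Power | 90% | just over 80% |
| Number per group before losses | 10 | 26 |
| Attrition | 10% | 15% |

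**The concern.** A synopsis may be shorter than the statistical section, but it should not describe a different calculation. Here the paragraph labelled as the rationale for 60 does not lead to 60, and nothing in the protocol says how 10 per group becomes 30.

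Read alone, the synopsis tells an ethics committee or funder that 10 per group would be enough, so 30 per arm looks three times too large. It also gives a type II risk of 10%, for 10 units. The calculation that yields 60 carries a risk of about 19%, for 4.4 units. A null result would be read differently depending on which difference the trial was designed to detect. This matters for a pilot whose stated purpose is to inform pivotal trials.

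**Working it through.** **Method.** Two-sample t-test, 1:1 allocation, two-sided alpha 0.05. With n per group and d = difference / SD, power comes from the noncentral t distribution with 2n − 2 degrees of freedom and noncentrality d√(n/2). All inputs are printed in Sections 1.0 and 8.9.

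**1. Section 8.9.**
- d = 4.4 / 5.5 = 0.8. At 26 per arm, power is 80.7%, which matches the claim of more than 80%.
- Attrition: 52 × 1.15 = 59.8, which rounds to the stated 60. Dividing instead, 52 / 0.85 = 61.2, which rounds up to 62.
- Conversely, 60 × 0.85 = 51 evaluable, and 26 against 25 gives 79.9%. Keeping 52 of 60 corresponds to a loss of 1 − 52/60 = 13.3%.

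Section 8.9 therefore reproduces to within one or two patients.

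**2. Synopsis.**
- d = 10 / 5.5 = 1.818.
- Normal approximation: n = 2 × [5.5 × (1.960 + 1.282) / 10]² = 6.36, so 7 per group.
- Exact t-test solution: 7.46, so 8 per group.

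| Per group | Power for 10 units, SD 5.5 |
|---|---|
| 7 | 87.7% |
| 8 | 92.2% |
| 9 | 95.1% |
| 10 | 97.0% |
| 30 | above 99.99% |

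- With 10% drop-out, 8 / 0.9 = 8.9, so 9 per group (18 in total). The printed 10 gives 10 / 0.9 = 11.1, so 12 per group (24 in total).
- Multiplying by 1.10 instead gives 9 and 11 per group, 18 to 22 in total. If the printed 10 already includes drop-out, the total is 20.
- One-sided testing, 80% power and the normal approximation all give smaller totals. No variant comes near 60.

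**3. Could one rationale stand in for the other?**
- 10 per group has 39.5% power for 4.4 units.
- 90% power for 4.4 units needs 34 per arm (33 gives 89.3%, 34 gives 90.2%). That is 68 before losses, and 68 × 1.15 = 78.2 to 68 / 0.85 = 80 after them.
- At SD 5.5, 60 less 10% leaves 27 per arm, which has 90% power for d = 0.899, that is 0.899 × 5.5 = 4.9 units, about half of 10.
- For 10 units to require 27 per arm at 90% power, the SD would have to be 10 / 0.899 = 11.1, twice the value stated in both places.

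The gap is too large for rounding or a choice of formula to explain.

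**The case against.** The case for treating this lightly is that 60 is the same everywhere, Section 8.9 and Table 4 agree with each other and support it, and only one synopsis paragraph is out of line. That is true. It limits the remedy to that paragraph, but does not make the paragraph right.

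The range of 18 to 24 depends on the drop-out convention and on whether the printed 10 is before or after losses. This also stands, but the alternatives give 18 to 22, or 20, so the conclusion is unaffected. Section 8.9 itself reaches 60 only with the multiplying convention; dividing gives 62. It still lands close to 60, which the synopsis does not.

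The two type II risks refer to different differences, so 10% against 19% is not a like-for-like comparison. For 10 units, 30 per arm has power above 99.99%. The point is narrower: the stated 10% does not belong to the calculation that sized the trial.

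The weightiest objection is that adopting 4.4 units chooses a target for the sponsor. Section 8.9 obtains 4.4 simply as 0.8 × 5.5. Section 7.1.2.2.2 puts the minimal clinically important difference at 15 to 20%, which at the 33.3-second entry threshold is 5.0 to 6.7 seconds; 4.4 is 13% of 33.3. So the protocol does not establish 4.4 as the clinically intended difference, and the sponsor should confirm it. It remains the only difference from which the protocol derives 60.

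**Conclusion.** The concern holds. The synopsis inputs give 8 to 10 per group and about 18 to 24 patients in total, against a stated 60. The Section 8.9 calculation gives 80.7% power at 26 per arm and about 60 enrolled. The two differ in target difference, power, number per group and attrition, and nothing in the protocol reconciles them.

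This rests on a two-sample t-test with the printed SD of 5.5. It does not show that 60 is too small under the Section 8.9 assumptions. The defect is a sample-size rationale that is wrong as written. The part of Section 4.1 under the Preliminary Results heading was not available here; it may explain where 10 units or 5.5 came from, but it could not make the synopsis arithmetic lead to 60.

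**What to change.** Replace the synopsis rationale with the Section 8.9 calculation: two-sided alpha 0.05, about 80% power, 4.4 units (d = 0.8, SD 5.5), 26 per arm, 15% attrition, 60 enrolled. The sponsor should confirm that this is the intended target difference. If 10 units was intended, the basis for 60 has to be restated in all three places.

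Two small edits are optional. Because 15% attrition from 60 leaves 51 (79.9%), write about 80% power, or give the attrition as about 13%. Also say whether 5.5 is the SD of the 9HPT or of its change, unless Section 4.1 already does.

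The cost is one paragraph. The synopsis will then show about 80% power rather than 90%, and 4.4 units rather than 10. No patients are added, no new data are collected and the analysis is unchanged.

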7.1.1.1.1 General Informed Consent

Consent will be documented by the subject's dated signature on a consent form along with the dated signature of the person conducting the consent discussion.

A copy of the respective signed and dated consent forms (subject consents) will be given to the subject and subject before participation in the trial.

The initial subject informed consent forms, any subsequent revised written informed consent forms and any written information provided to the subject will receive the Ethic Committee of the Hospital del Mar approval/favorable opinion in advance of use. The

subjects will be informed in a timely manner if new information becomes available that may be relevant to their willingness to continue participation in the trial. The communication of this information will be provided and documented via a revised consent form(s) or addendum to the original consent form(s) that captures the subject's dated signature.

Relevant clinical or MRI findings will be disclosed to the patient and refer for appropriate care.

Specifics about a trial and the trial population will be added to the consent form template(s) at the protocol level. Informed consent(s) will adhere to the ethics Committee requirements, applicable laws and regulations.

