7.1.1.3 Subject Identification Card

All subjects will be given a Subject Identification Card identifying them as participants in a research trial. The card will contain trial site (Hospital del Mar) contact information (including direct telephone numbers) to be utilized in the event of an emergency. The investigator or qualified designee will provide the subject with a Subject Identification Card immediately after the subject provides written informed consent.

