7.2.5 Investigator Responsibility for Reporting Adverse Events

All Adverse Events will be reported to the Ethical Committee of Hospital del Mar and investigators in accordance with all applicable global laws and regulations, i.e., per ICH Topic E6 (R1) Guidelines for Good Clinical Practice.

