10.2.1 Compliance with Ethical Principles and Medical Device Regulation

This study will be conducted in accordance with the ethical principles outlined in the Declaration of Helsinki, as adopted by the 75th World Medical Assembly, Helsinki, Finland, October 2024, and any subsequent revisions.

In addition, the study will comply with all applicable regulatory requirements, including the Regulation (EU) 2017/745 on medical devices, specifically concerning clinical investigations involving medical devices.

The protocol, informed consent forms, and any other relevant study documentation will be reviewed and approved by an independent Ethics Committee prior to initiation. All participants will provide written informed consent before any study-related procedures are performed.

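### Section 7.1.1.3 gives every participant a card with Hospital del Mar as the only stated emergency contact, although the trial also recruits in the Netherlands

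*Protocol*

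**What the plan says.** The Trial Outline (section 1.0) describes the sites in two rows.

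- **Study Schedule.** Patients in Spain come from three Barcelona hospitals and are "treated in a single therapy center at Hospital del Mar located closely to all of them". The next sentence adds the second country: "Patients in the Netherlands are recruited at the Rijndam center, Erasmus Medical Center".
- **Study Center.** The list repeats the four centres and ends "Hospital Sant Pau (HSP), all in Barcelona, Spain; Rijndam center, Erasmus Medical Center (EMC").

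Section 7.1.1.3 then sets the rule for the identification card. On who receives it: "All subjects will be given a Subject Identification Card identifying them as participants in a research trial". On what it shows: "The card will contain trial site (Hospital del Mar) contact information (including direct telephone numbers) to be utilized in the event of an emergency". It is handed over by the investigator or a designee, directly after written consent.

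Two other sections name the same institution. Section 7.1.1.1.1 says that consent forms and written participant information "will receive the Ethic Committee of the Hospital del Mar approval/favorable opinion in advance of use". Section 7.2.5 (Investigator Responsibility for Reporting Adverse Events) says "All Adverse Events will be reported to the Ethical Committee of Hospital del Mar and investigators", and goes on to require that this follow the applicable laws and regulations. Section 10.2.1 is more general: the protocol, consent forms and other study documents "will be reviewed and approved by an independent Ethics Committee prior to initiation".

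**The concern.** The synopsis and the card rule do not fit together. The synopsis has a Dutch centre and ties treatment at Hospital del Mar to patients in Spain. The card rule covers every subject and equates the trial site with Hospital del Mar.

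The Dutch centre is also part of the statistical design: randomization is stratified by center (section 5.4), and the mixed model has a random intercept for site (section 8.1). Section 7.1.1.3 appears to be single-site wording that was not revised for a second country.

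At stake is whom a participant, a relative or an emergency clinician reaches when they use the card during a blinded stimulation trial. For someone enrolled through the Dutch centre, the number given would lead to a hospital abroad, and the protocol does not say that Hospital del Mar staff would hold that person's records. Safety and tolerability is Objective 1 in section 3.1, so the participant's emergency contact should be right at every centre.

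**Working it through.** No arithmetic applies, and the protocol gives no figure to reproduce. The check sets the relevant sections side by side.

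**Step 1: who is in the trial.** Section 1.0 lists four recruiting centres, three in Barcelona and one in the Netherlands.

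**Step 2: where Hospital del Mar is the treating site.** The sentence that places treatment there has patients in Spain as its subject. The Dutch patients have their own sentence, which says where they are recruited and does not send them to Barcelona.

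**Step 3: what the card rule covers.** Section 7.1.1.3 applies to all subjects, with no exception by country or centre, and names one institution as the emergency contact.

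**Step 4: combine.** Steps 1 and 3 together mean that a participant enrolled through the Dutch centre gets a card with Hospital del Mar's details. By step 2, the protocol nowhere makes Hospital del Mar that participant's site.

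**Step 5: look for a correction elsewhere.**

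| Section | What it covers | Does it correct the card? |
|---|---|---|
| 7.1.4.2 Blinding/Unblinding | Investigator's route to a call centre, with IVRS/IWRS as fallback where a site has no call centre | No. It serves investigators, not card holders |
| 7.2.3.1 Serious Adverse Events | Reporting clock, starting when the site becomes aware | No. It concerns reporting |
| 7.2.5 Management and Reporting of Adverse Events | SAEs to the sponsor within 24 hours by EDC or paper; other AEs in the case report forms | No. It concerns reporting |
| 10.2.1 Ethical principles and device regulation | Independent ethics committee approval | No. The card is not mentioned |

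**Step 6: test the two ethics committee passages in the same way.** Sections 7.1.1.1.1 and 7.2.5 (Investigator Responsibility for Reporting Adverse Events) each name the Hospital del Mar committee. Neither says that it alone acts. Both defer to applicable laws and regulations, and 10.2.1 requires independent ethics approval without exempting any site. These passages are therefore incomplete for a two-country trial, but they do not contradict it as the card rule does.

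**The case against.** The best case for leaving the text alone has four parts.

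1. **The card rule is not exclusive.** Section 7.1.1.3 says what the card will contain. It does not forbid a local number or tell participants to avoid local care, and a Dutch investigator would hand the card over. This is fair as far as it goes, but the section defines the trial site as Hospital del Mar and offers no other contact. A site that follows the protocol to the letter prints the Barcelona number alone.

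2. **The protocol does contemplate several sites.** Stratification by center and the site-specific fallback for unblinding show this. The point stands, so it would be wrong to say that the operating sections as a whole describe a single-site trial. It does not change the wording of the card rule.

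3. **The treating site of Dutch patients is not stated.** The synopsis says only that they are recruited at the Dutch centre. Treatment there is a natural reading, but it remains an inference.

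4. **Some text is not available.** Contact pages and the confidentiality section were removed from the copy reviewed, and committees or site contacts may be named there. This is a reason for caution about any claim that no Dutch committee is named. It does not alter the explicit words of 7.1.1.3.

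A reader might go further and infer that AEs or SAEs would be recorded late at the Dutch centre. The documents do not support that. Investigators monitor participants at visits and treatment sessions, SAEs go to the sponsor by EDC or paper, and the clock starts at site awareness. None of these routes depends on the card or on which ethics committee is named.

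**Conclusion.** The point holds for the identification card. Section 7.1.1.3 states a rule for all subjects that does not suit the Dutch centre in section 1.0, and nothing in the available text corrects it. Because the rule is stated and wrong for one centre, it is more than a missing detail.

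**Size.** Every participant recruited at one of four listed centres is affected. Of the planned 60, the number enrolled in the Netherlands is not given. A reader might divide equally and arrive at 15 (60 / 4), but the protocol states no split by centre, so that figure has no basis.

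**Assumptions.** The conclusion takes section 7.1.1.3 as written and supposes that people recruited at the Dutch centre spend the trial mainly in the Netherlands. It does not require that they be treated there.

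**Limits.** The effect is on safety logistics. Randomization, the primary endpoint and the efficacy analysis are untouched. A reader might also infer that Dutch participants would lack ethics oversight. The text does not show this: naming one committee does not exclude others, and section 10.2.1 requires independent ethics approval. The committee wording needs only a minor consistency edit.

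**What to change.** **Main change, section 7.1.1.3.** Replace the parenthesis naming Hospital del Mar with the emergency contact of the participant's own trial site. Hospital del Mar may stay on the card as coordinating contact. The cost is a card template with a site-specific field.

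**Minor consistency edit, sections 7.1.1.1.1 and 7.2.5 (Investigator Responsibility for Reporting Adverse Events).** Replace the single named committee with wording that fits two countries, for example the responsible ethics committee for each site. The cost is a change of wording in two places.

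Neither change adds participants, visits or procedures, and neither affects the analysis.
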